Study Protocol

With the approval of the XXXXXX Clinical Research Ethics Committee dated 26.12.2023 (No. 2023-172) and registration on ClinicalTrials.gov (NCT06241794), this study commenced. The study was conducted as a prospective, randomized, and blinded trial in the operating rooms of XXXXXXXXX Hospital between 01.01.2024 and 01.05.2024. A total of 72 patients, aged 18-65, classified as ASA (American Society of Anesthesiologists) physical status I-II, who were scheduled for laparoscopic cholecystectomy by the general surgery clinic, were included in the study after obtaining written and verbal consent. The study was designed and conducted in accordance with the ethical principles set forth in the Declaration of Helsinki.

Patient randomization was performed using an internet-based software program (Research Randomizer, http://www.randomizer.org/). Patients were randomly assigned to two groups based on the type of nerve block performed:

- Group 1 (n=35): Patients who received a modified thoracoabdominal nerve block via a perichondrial approach (M-TAPA)

- Group 2 (n=37): Patients who received a serratus intercostal plane block combined with a rectus sheath block (SIPB + RSB)

Inclusion criteria:

- Scheduled for laparoscopic cholecystectomy due to cholelithiasis
- ASA physical classification I-II
- Age between 18-65 years
- Body mass index (BMI) <35
- Patients who read and accepted the informed consent form

Exclusion criteria:

- Patients unwilling to participate
- ASA physical classification III or higher
- BMI >35
- Patients unable to score pain using the NRS system

- Patients with allergies to the local anesthetic and analgesic drug used
- Pregnant and breastfeeding patients
- Patients under 18 or over 65 years of age
- Patients with uncontrolled anxiety
- Patients with alcohol and drug addiction
- Patients with neuromuscular diseases and peripheral nerve disorders
- Patients with widespread chronic pain
- Patients with hepatic and renal failure
- Patients with contraindications for peripheral block
- Patients undergoing a second procedure along with laparoscopic cholecystectomy
- Patients with a history of abdominal surgery or trauma
- Patients where laparoscopic surgery was converted to open surgery
- Patients with technical issues using patient-controlled analgesia (PCA) devices
- Patients unable to understand or complete the Quality of Recovery-15 (QoR-15) scale

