Following the completion of the block procedures, neuromuscular blockade was reversed with 4 mg/kg sugammadex (Brimadex, Polifarma ilaç, Tekirdağ) under 80% O2 ventilation. Patients with adequate spontaneous respiration were extubated and transferred to the recovery room. Patients' vital signs, pain scores, and postoperative nausea and vomiting (PONV) scale were monitored in the recovery room. Pain assessment using the numerical rating scale (NRS) was performed at rest (static) and during active movement (transitioning from lying to sitting - dynamic). Pain intensity was rated from 0 (no pain) to 10 (worst imaginable pain). For postoperative analgesia, iv tramadol PCA was administered. The PCA protocol was set to 10 mg bolus tramadol on demand with a 20-minute lockout period without basal infusion. Tramadol consumption was recorded at 0-1 hour, 0-12 hours, 12-24 hours, and the total at 24 hours. Patients with a pain score above 4 in the recovery room received 25 mcg iv fentanyl as rescue analgesia, which was recorded.

Patients with an Aldrete score of 9 or higher were transferred to the ward. Postoperative pain follow-up was conducted by an anesthetist blinded to the group assignment. NRS scores were recorded at 0, 1, 3, 6, 12, 18, and 24 hours postoperatively. All patients received 1 g iv paracetamol every 8 hours for postoperative analgesia. Patients with pain scores above 4 despite the analgesic regimen received 50 mg iv dexketoprofen (Ketavel, Deva İlaç, Kocaeli) as rescue analgesia.

To determine the sensory block's dermatomal level, pinprick testing was performed at 2 and 24 hours postoperatively using a sterile needle along a vertical line 3-5 cm away from the midline and mid-axillary line between the T3-L1 sensory levels. A three-point numerical scale (0 = no prick sensation, 1 = reduced prick sensation, 2 = normal prick sensation) was used. Scores of 0 or 1 were considered effective. Normal sensation in the shoulder was used for comparison.

Patients were monitored for PONV within the first 24 hours postoperatively using a scale (PONV 1: no nausea or vomiting, PONV 2: nausea but no vomiting, PONV 3: single episode of vomiting or persistent nausea, PONV 4: two or more episodes of vomiting or severe/persistent retching). Patients with a PONV score of 2 or higher received 4 mg iv ondansetron. The total ondansetron dose administered within the first 24 hours postoperatively was recorded.

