Patients completed the QoR-15 (Quality of Recovery-15) questionnaire, a self-report measure of postoperative recovery quality, twice: once in the waiting area on the morning of surgery and again 24 hours postoperatively. The time to first oral intake, time to first flatus/stool, and time to first mobilization (standing unaided) within the first 24 hours postoperatively were recorded.

Statistical Methods

The statistical analyses of the data obtained in this thesis were performed using the SPSS software package (Version 22.0, SPSS Inc., Chicago, IL, USA - Licensed by Hitit University). Descriptive statistics were presented as mean \pm standard deviation for continuous data showing normal distribution, median (min-max) for continuous data not showing normal distribution, and number and percentage (%) for categorical data. The normality of the data distribution was analyzed using Shapiro-Wilk tests. To compare the means of two independent samples of continuous variables, the independent samples t-test was used for normally distributed data, and the Mann-Whitney U test was used for data not normally distributed. For comparisons of two dependent groups of continuous variables, the paired t-test was applied for normally distributed data. The Friedman test was used for comparing numerical variables among more than two dependent groups with data not normally distributed. After variance analysis, Bonferronicorrected post-hoc tests were applied to determine the source of differences among groups. Relationships between categorical variables for two independent groups were evaluated using the Chi-square test or Fisher exact test, depending on the cell counts in cross-tabulations. Statistical significance was set at p<0.05.

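### No outcome is named as primary and one unadjusted 0.05 threshold covers every comparison of the two blocks, so any single nominal result could be read as showing one block better

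*Combined protocol and SAP*

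**What the plan says.** The Statistical Methods name a test for each type of data. For continuous outcomes in the two arms, "To compare the means of two independent samples of continuous variables, the independent samples t-test was used for normally distributed data", with Mann-Whitney U otherwise; categorical outcomes get chi-square or Fisher's exact test. The section ends with a single threshold, "Statistical significance was set at p<0.05".

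The one mention of multiplicity comes after the method for repeated measurements. "The Friedman test was used for comparing numerical variables among more than two dependent groups with data not normally distributed", and then "After variance analysis, Bonferronicorrected post-hoc tests were applied to determine the source of differences among groups".

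The Study Protocol section describes the outcomes in the order in which they were collected. On pain, "Pain assessment using the numerical rating scale (NRS) was performed at rest (static) and during active movement" and "NRS scores were recorded at 0, 1, 3, 6, 12, 18, and 24 hours postoperatively". It goes on to tramadol in four windows, rescue fentanyl and dexketoprofen, pinprick level, nausea and vomiting, ondansetron dose, QoR-15, and times to oral intake, bowel function and mobilization. None is called primary, main or secondary. No hypothesis, testing order or sample-size calculation is given from which a primary could be inferred.

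The opening paragraph points to two outside records: "With the approval of the XXXXXX Clinical Research Ethics Committee dated 26.12.2023 (No. 2023-172) and registration on ClinicalTrials.gov (NCT06241794), this study commenced". The study ran at the "Hospital between 01.01.2024 and 01.05.2024".

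**The concern.** A trial of two blocks needs one stated comparison that decides whether one is better. Here roughly two dozen recorded outcomes could be compared between arms, all on the same footing and each at 0.05. The plan states no criterion for superiority and no adjustment across outcomes, so nothing in it stops the most favourable comparison from being presented as the finding. Two consequences follow. The chance of a false positive conclusion is well above the nominal 5%, and a reader cannot tell an intended result from one picked out afterwards.

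The documents report no results, so this is a gap in the plan and not evidence that any result was misused.

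**Working it through.** **The plan's own figures.** The only error-rate figure is the 0.05 threshold, a convention with nothing behind it to reproduce. Its sidedness is not stated; two-sided is assumed below. The arm sizes agree with the total: 35 + 37 = 72.

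**Does the Bonferroni sentence help?** It follows the Friedman test for more than two dependent groups, so it most naturally concerns time points within patients. With two arms there is no between-arm post-hoc test for it to correct. Even read generously, it does not adjust across different outcomes.

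**How many comparisons?** The plan lists outcomes, not tests, so the count is the reviewer's.

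| Outcome | Count | Basis |
|---|---|---|
| NRS, rest and movement, 7 times | 14 | assumes both conditions at every time, each time compared |
| Tramadol windows | 4 | overlapping |
| Rescue fentanyl, dexketoprofen | 2 | recording of dexketoprofen is assumed |
| PONV, ondansetron dose, QoR-15 | 3 | stated |
| Recovery times | 3 | stated |
| Total | 26 | pinprick levels not counted |

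Two shorter counts:
- Without NRS: 26 − 14 = 12.
- Also without three tramadol windows and dexketoprofen: 12 − 4 = 8. This leaves 24-hour tramadol, fentanyl, PONV, ondansetron, QoR-15 and three recovery times.

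**Chance of at least one p<0.05 when the arms differ on nothing.** For k independent tests this is 1 − 0.95^k. For a common correlation r, with u standard normal and Φ the normal distribution function, it is

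1 − E{[Φ((1.96 − √r·u)/√(1−r)) − Φ((−1.96 − √r·u)/√(1−r))]^k}.

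| k | independent | r=0.3 | r=0.5 | r=0.7 | r=0.8 | r=0.9 |
|---|---|---|---|---|---|---|
| 26 | 0.736 | 0.619 | 0.475 | 0.321 | 0.245 | 0.166 |
| 12 | 0.460 | 0.397 | 0.319 | 0.232 | 0.186 | 0.135 |
| 8 | 0.337 | 0.300 | 0.250 | 0.191 | 0.157 | 0.119 |

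The documents give no correlations, so these are illustrations. Leaving out dexketoprofen (k=25) gives 0.607, 0.467 and 0.316 at r = 0.3, 0.5 and 0.7, which changes nothing material.

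**Checks on the remedy** (r = 0.3, 0.5, 0.7 unless stated)
- Secondaries chosen after the results: in the worst case the three smallest p-values of 25 null outcomes are picked. Holm's first step is 0.05/3 = 0.0167, and the chance of at least one rejection is 0.277, 0.207 and 0.136. A Holm list therefore protects only if it was fixed beforehand.
- A prespecified primary at 0.05 plus three Holm secondaries tested regardless of the primary: 0.092, 0.085 and 0.073. If independent, 1 − 0.95 × (1 − 0.0167)³ = 0.097. If secondaries are tested only after a significant primary, the figure is 0.05 when no outcome differs.
- Power, noncentral t with 70 degrees of freedom, 35 v 37: an assumed effect of d = 0.67 has 0.80 at 0.05 and 0.65 at 0.0167. Requiring also that a primary with 80% power be significant brings the latter to about 0.52 (independent) to 0.60 (r = 0.7).

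**The case against.** The strongest objection is that the primary may exist elsewhere. The ethics approval predates the study start, and a registration number is given; either record could name a primary outcome. If one does, the defect shrinks to a missing statement in this text. That stands, and it confines the point to these documents. It does not repair them, because a reader of this text still cannot tell which comparison was meant to decide.

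Second, the harm is conditional. No result or superiority claim appears, and the text is written in the past tense. Rewriting the methods cannot restore prespecification if the analysis is done. This too stands, and is why the fix relies on an earlier dated record and otherwise falls back on exploratory labelling.

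Third, the count is generous and the formula simple:
- Static and dynamic scores at all seven times is an assumption.
- The 24-hour tramadol total should equal the sum of the two 12-hour windows.
- Ondansetron is triggered by the PONV score, so those two outcomes are linked by rule.
- Fisher's exact test is conservative, and one common correlation for pain, nausea and bowel recovery is unrealistic.

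These points weaken any single probability but not the direction. Merging PONV with ondansetron leaves 7 tests, which at r = 0.9 still give 0.11.

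Fourth, gated Holm testing is only one acceptable scheme, and the power loss above uses only its first, strictest step. If all three secondaries had d = 0.67, power per secondary would be about 0.74 to 0.77 ungated and 0.62 to 0.69 gated (simulation, normal approximation). Both points are fair. The Holm step is optional, and the 0.65 and 0.52–0.60 figures are the pessimistic case.

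**Conclusion.** The concern holds and must be fixed. This text names no primary outcome and leaves the two-arm comparisons unadjusted across outcomes. Confidence is high on those two facts, not on any one probability. Under the stated rule, with no true difference, the chance of at least one nominally significant result in the table ranges from 0.12 (8 tests, r = 0.9) to 0.74 (26 independent tests), against a nominal 0.05. The range rests on assumed counts and correlations. Whether the trial as a whole lacks a prespecified primary cannot be judged without the registration and the ethics submission.

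**What to change.** 1. Check the registration and the ethics submission for a primary outcome, and any key secondaries, recorded before outcomes were seen. The approval is dated 26.12.2023, before the 01.01.2024 start; this text gives no registration date, so that must be established.
2. If a primary is found, name it in the Statistical Methods as one between-arm comparison tested at two-sided 0.05.
3. Optionally, test a short list of key secondaries with Holm, only if the list comes from the same kind of dated record and only if the primary is significant.
4. Report all other outcomes as estimates with 95% confidence intervals and no significance claim. This includes NRS by time, the overlapping tramadol windows and any dermatome results.
5. If no earlier record names a primary, label all between-arm results exploratory and make no superiority claim from a single p<0.05.

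The cost is two record checks, rewording and confidence intervals; no new data are needed. A recovered primary keeps its full 0.05. The price is that some nominal results can no longer be claimed, Holm secondaries lose some power, and without an earlier record the trial supports no confirmatory claim.
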